### Aim

The aim of this study is to test the delivery of brief health promotion advice with supporting information leaflets as part of standard clinical consultation for older people attending a community mental health service.

Objectives: The main objectives are to;

- (a) to screen MH patients for frailty using validated tools the clinical frailty scale and SCAR-F
- (b) to test the feasibility of patient recruitment and data collection in the target population
- (c) determine the prevalence of frailty in older adults living with a mental health condition within an outpatient MH service
- (d) examine the acceptability of the brief health promotion advice and information leaflets as part of MH consultation
- (e) examine self-reported adherence to the exercise and nutrition advice at 1 and 3-month follow-up
- (f) Repeat frailty screening and overall physical and mental health at three month follow-up

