### Sample size

We aim to recruit 15-20 patients to test the feasibility of the intervention in this population.

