### Study Design

The study uses a one group pretest –posttest intervention design with patient survey at baseline, 1 month and 3 month follow-up. The project is undertaken over 12 months. Once ethical approval is obtained, patient recruitment and baseline data is collected and the intervention delivered: in March – June 2023, 1 month follow-up April to July and three month follow-up August to October 2023.

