#### Obtaining Consent

Participants provide written consent to the study. the ANP liaises with the Mental Health team to identify eligible patients and ensure the team are happy for the service user to be approached about the study.

Service Users receive an introduction letter and a copy of the patient information sheet informing them of the study and advising that they may be asked to participate in the study at their next outpatient appointment or home visit. The patient meets the data collector who explains the study, answer any questions and obtains written consent.

Participants are given the right to withdraw from participation should they wish to, as well as to opt out of answering questions. Participants have a right to withdraw without explanation. Patients provide permission to collect identifying information to allow follow-up. As soon as follow-up is complete, all identifying information is removed from the dataset so the data becomes de-identified and the participant is allocated a study ID.

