In the past week (7 days) have you completed the exercises on the information leaflet

Frequency (None=0, 1 day=1, 2 days=2; 3 days=3, 4 days=4, 5 days=5); X Duration (none =0; 10 mins=1, 11-20 mins=2, 21-30 mins=3, >30 mins=4). Higher values indicate greater exercise intensity (min score 0 to 20).

Nutrition: Simplified nutritional appetite questionnaire (SNAQ) is a four item scale (rate appetite, When I eat I feel full, food tastes, normally I eat) are rated on a five point scale (1 to 5). Total possible score range from 5 to 20, higher scores indicate better appetite. SNAQ score 14 indicates significant risk of at least 5% weight loss within six months (Kruizenga et al., 2005).

Protein intake: Patients self-reported the number of protein portions eaten in the previous day: Protein was categorised as: meat/fish; milk/dairy; eggs/cheese; vegetable protein

The one-month questionnaire focused on acceptability of intervention and ease of use.

Patients are also be asked to give qualitative feedback on the intervention.

The 3-month questionnaire repeated the baseline measures and adherence questions.

Implementation outcomes:

Acceptability (Bespoke item)

One item measures acceptability: The exercise and nutrition advice was acceptable to me (made sense) rated on a 5 point Likert scale (1=strongly disagree to 5 strongly agree)

Ease of Use (Bespoke item)

One item measured Ease of Use ' To what extent was it easy to incorporate the exercise and nutrition advice into your daily routine rated on a five point Likert scale (1=very difficult to 5 very easy)

Recommend to others (bespoke item)

The final item sought participants opinion on 'recommending the intervention to others. 'In your opinion, should we continue to offer this advice and information leaflets to other people attending our service? With three response options Yes/No/ Don't know

A study log is maintained recording the number of eligible patients invited to participate, the number of patients who refused, reasons for refusal, number of patients who consented, number of patients who completed 1-month and 3-month follow-up.

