### Analysis

Data analysis uses descriptive statistics. Categorical data is presented as proportions and percentages, continuous data as medians inter quartile ranges. Non-parametric paired statistics is used to compare the pre and post data, however sample size is too small for a comprehensive analysis.

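### Acceptability and adherence come only from patients who answer at follow-up; with no denominator rule and no reasons for loss after consent, any loss caused by the advice would flatter the figures unseen

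*Combined protocol and SAP*

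**What the plan says.** The study is a "one group pretest –posttest intervention design with patient survey at baseline, 1 month and 3 month follow-up", and the Sample size section states: "We aim to recruit 15-20 patients to test the feasibility of the intervention in this population". The advice and leaflets are given at the baseline consultation.

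- **Timing of the items.** In the Outcomes section: "The one-month questionnaire focused on acceptability of intervention and ease of use". Objective (e) in the Aim section is to "examine self-reported adherence to the exercise and nutrition advice at 1 and 3-month follow-up", and the Outcomes section adds: "The 3-month questionnaire repeated the baseline measures and adherence questions". The item on offering the advice to others has no named time point.
- **Leaving the study.** Under Obtaining Consent: "Participants have a right to withdraw without explanation". The same paragraph also lets participants decline individual questions. The Patient Safety Protocol gives a second route to missing data: study data collection stops if the patient deteriorates.
- **The log.** Before consent it holds invitations, refusals and reasons for refusal. After that it holds the "number of patients who consented, number of patients who completed 1-month and 3-month follow-up", without reasons.
- **Reporting.** The Analysis section says: "Categorical data is presented as proportions and percentages". It names no denominator, no rule for missing answers and no sensitivity analysis.
- **Retention.** Under Data management, the study register and paper questionnaires are destroyed after follow-up and data verification.

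**The concern.** Acceptability and adherence are objectives (d) and (e), so they are among the main things this study can report. The exercise is unsupervised, and giving it up is itself a finding about acceptability. A patient who disengages in the first month has received the advice in full, yet may be absent from every item designed to detect that it did not suit.

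If percentages are taken over those who answered, which is what happens when no rule is written, advice-related loss removes unfavourable opinions from both numerator and denominator. A report could then show near-universal acceptance while some of those given the advice had abandoned it. Reasons for loss are not logged, and the linking register and questionnaires are later destroyed, so the cause could not be recovered afterwards. It has to be captured at the time.

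**Working it through.** The documents give no attrition rate, acceptability target or sample-size calculation, so there is no planned figure to reproduce. The check asks how far a respondents-only percentage can differ from the percentage of all patients given the advice.

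**Inputs.** N = 15 or 20, the recruitment aim in the Sample size section. m = patients with no answer; 0 to 5 is assumed because the documents give no figure. x = favourable answers; a cut-point such as agree or strongly agree is assumed, because the plan sets none. Consented patients and patients given the advice are treated as the same group.

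**Formulas.**
- Respondents only: x / (N − m)
- All given the advice, every missing answer unfavourable (lower bound): x / N
- All given the advice, every missing answer favourable (upper bound): (x + m) / N

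The bounds are m/N apart, so each lost patient widens the range by 1/20 = 5.0 points or 1/15 = 6.7 points.

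**Examples.**

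| N | m | x | Respondents only | Lower bound | Upper bound |
|---|---|---|---|---|---|
| 20 | 4 | 15 | 15/16 = 93.8% | 15/20 = 75.0% | 19/20 = 95.0% |
| 20 | 3 | 15 | 15/17 = 88.2% | 15/20 = 75.0% | 18/20 = 90.0% |
| 15 | 3 | 11 | 11/12 = 91.7% | 11/15 = 73.3% | 14/15 = 93.3% |

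In the first row the respondents-only figure lies 93.75 − 75.0 = 18.75 points above the lower bound but only 95.0 − 93.75 = 1.25 points below the upper bound. When respondents are nearly unanimous, almost all the room for error is downward.

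**If every respondent is favourable**, the respondents-only figure is 100% whatever the loss. The lower bound is then (N − m)/N:

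| Lost | 0 | 1 | 2 | 3 | 4 | 5 |
|---|---|---|---|---|---|---|
| N = 15 | 100% | 93.3% | 86.7% | 80.0% | 73.3% | 66.7% |
| N = 20 | 100% | 95.0% | 90.0% | 85.0% | 80.0% | 75.0% |

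With no loss the figures coincide.

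**Can the data collected narrow the range?** The log gives N and N − m, so the bounds can be calculated. It gives no reasons for the m losses, so the report could not say which end is more plausible.

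**The case against.** The strongest reply is that the plan already makes room for patients who dislike or abandon the advice. They remain in the service, and follow-up can be by telephone or at routine contacts. The 1-month contact is meant to examine adherence, the rating scales have negative ends, the leaflet item has a zero category, and qualitative feedback is sought. All of this stands, and it may keep losses small. It does not help for a patient who gives no follow-up answers.

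The reply also defeats several stronger readings that a reader might infer:

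- *Withdrawal is all-or-nothing.* The documents do not say so. Participants may skip questions, and nothing treats stopping the exercises or diet as leaving the study. The gap is that the two are not distinguished.
- *The percentages can only be of respondents.* The log counts patients consented and patients completing each follow-up, so the wider denominator can be rebuilt. Respondents-only is a default, not a written choice.
- *The results will be biased upward.* That depends on some patients leaving because of the advice. Loss through deterioration or other causes need not raise the figure.
- *Count every non-respondent as unfavourable or non-adherent.* That is a lower bound, not an estimate. It would record a patient lost through deterioration as rejecting the advice. Nor does it fit the leaflet score, which runs from 0 to 20 with no adherence threshold.
- *The respondents-only figure is the upper bound.* It is not, unless all respondents are favourable: 93.8% against 95.0% in the first example.

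**Conclusion.** The point holds as a conditional one. Acceptability, ease of use and adherence, and by inference the recommendation item, come only from patients who answer at follow-up. The plan states no denominator and records no reason for loss after consent. If any loss is advice-related, the default percentages lean favourable and the data could not reveal it.

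The size cannot be fixed from the documents. Each lost patient adds 5.0 to 6.7 points of uncertainty. In the assumed case of 4 lost from 20 with 15 of 16 agreeing, 94% of respondents corresponds to 75% to 95% of all given the advice. This rests on the assumed loss and on an assumed cut-point for a favourable rating. The Analysis section does not say whether the five-point ratings will appear as percentages or medians; medians would also omit lost patients.

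This does not invalidate a small descriptive feasibility study. It is a cheap improvement that changes what the study can conclude about acceptability.

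**What to change.** 1. **Outcomes, study log.** Add a voluntary reason for non-completion after consent: stopped following the advice, withdrew from follow-up, clinical deterioration, other, not given. The last category preserves the right to leave without giving a reason.
2. **Obtaining Consent and Outcomes.** State that stopping the exercises or diet is not withdrawal from the study. Such patients are still asked the 1- and 3-month items and their own answers are used, with no score assigned by assumption.
3. **Outcomes, implementation items.** Offer patients who leave follow-up the three one-line items on acceptability, ease of use and recommendation, with the right to decline.
4. **Analysis.** Report each implementation outcome as the number favourable among respondents and among all patients given the advice, with a lower bound (all missing unfavourable) and an upper bound (all missing favourable). State the rating that counts as favourable. For adherence, give the number answering out of all given the advice. List losses through deterioration separately.

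The cost is one log column and a few sentences of analysis text, with no extra visits or patients. The downside is a wider, less favourable headline range.

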#### Outcomes:

Sarcopenia: The SARC-F (tool title not an abbreviation) is a screening tool for sarcopenia ((Malmstrom et al 2013). SARC-F comprises five components using self-report on: strength, assistance walking, rise from a chair, climb stairs, and falls. SARC-F scale scores range from 0 to 10 (i.e. 0–2 points for each component; 0 = *best* to 10 = *worst*) and are dichotomized to represent symptomatic (4+) vs. healthy (0–3) status (Malmstrom et al 2016).

Frailty: Clinical Frailty Scale (CSF) is a judgement-based frailty tool that evaluates specific domains including comorbidity, function, and cognition to generate a frailty score ranging from 1 (very fit) to 9 (terminally ill), a higher score indicates poorer physical and cognitive function (Rockwood et al 2005, Church 2020).

The Global Physical Health Scale v1.2 is a four-item validated general health questionnaire (Riley et al 2010, Hays et al 2015). Four items are used to assess global physical health. Three items (rate your physical health, everyday activities, rate your fatigue) of these are administered using five-category response scales. Higher scores indicated better health. One item (rating of pain on average) uses a response scale of 0–10 that is recoded to five categories (0 = 1; 1-3 = 2; 4-6 = 3; 7-9 = 4; 10 = 5), the scale is then reverse coded, i.e. 0 (no pain) = 5). Overall scores range from 5 to 20 indicating best possible physical health (PROMIS 2021)

Mental health: Bespoke mental health items. Two items (rate your overall mental health, rate your mood (sense of well-being) over past seven days) were rated on a 5 point scale (excellent = 5; very poor = 1). Items are presented separately, scores range from 1 to 5, higher score indicates better mental health.

Exercise: Two items from Yale Physical Assessment Scale (vigorous exercise frequency and duration over past 7 days, and Walking for exercise frequency and duration over past 7 days) ((De Abajo et al., 2001). Frequency was rated on a 4 point scale (not at all=0; 1-2 times=1, 3-4 times=2 or >4 times=3) Duration (0=not applicable, 1=10-30 mins, 2=31-60 mins, 3> 60 mins. Scores are calculated by multiplying Frequency score X Duration score (no weight was applied). Higher scores indicate more activity. Items were not combined for an overall exercise score.

Post intervention, we added an additional question specific to the exercises on the information leaflet

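### The ease-of-use item has no 'did not try' response, so its 1–5 rating mixes experience of the advice with non-experience

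*Combined protocol and SAP*

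**What the plan says.** Under Implementation outcomes in the Outcomes section, ease of use is one bespoke item: "To what extent was it easy to incorporate the exercise and nutrition advice into your daily routine rated on a five point Likert scale", scored "1=very difficult to 5 very easy". It belongs to the 1-month contact: "The one-month questionnaire focused on acceptability of intervention and ease of use".

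Other items do provide for a patient to whom the question does not apply, or who cannot answer:

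- The item on recommending the advice: "With three response options Yes/No/ Don't know".
- The baseline exercise items: "Duration (0=not applicable, 1=10-30 mins, 2=31-60 mins".
- The leaflet-exercise item, asked about the past seven days: "Frequency (None=0, 1 day=1, 2 days=2; 3 days=3, 4 days=4, 5 days=5".

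Obtaining Consent allows participants to withdraw, "as well as to opt out of answering questions". The Analysis section says "Categorical data is presented as proportions and percentages", with medians and interquartile ranges for continuous data. It gives no denominator for the ease item and no rule for a blank answer.

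**The concern.** The item is in the past tense and presumes an attempt. Non-starters are foreseeable: the Exclusion Criteria describe the intervention as unsupervised, and the leaflet item has a code for having done none of the exercises. A non-starter who reaches follow-up can leave the item blank, and so drop out of its denominator, or can give a number between 1 and 5 that looks like any other rating.

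The setting could push such a number upwards. The nurse who delivers the advice also completes the questionnaire with the patient and is not blinded (Intervention components, Data collection, Data management). The 1-month contact is also meant to encourage adherence.

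At stake is what the ease rating describes. Of the three closed implementation items, it is the one that asks about putting the advice into practice. It should be clear whether the rating comes from patients who did so.

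**Working it through.** **Is there a plan figure to reproduce?** No. The plan gives no expected ease rating, success threshold or non-start rate, and 15–20 is stated without a calculation. What can be checked is how far the result depends on what non-starters do with the item.

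**Inputs.**
- N, patients followed up: 15 to 20 (Sample size), taking everyone to reach 1 month.
- k, non-starters among them: not in the documents; assumed.
- a, triers who rate 4 or 5: assumed. The 4–5 cut is also an assumption, because the plan does not dichotomise the item.
- Triers' ratings, needed for the medians: assumed to repeat the sequence 4, 5, 4, 3, 4, 2, 5, 4, 3, 3.

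**Formulas.** Let f = k/N and p = a/(N − k). The share rating 4–5 is then:
- non-starters leave it blank: a/(N − k) = p
- non-starters rate 1–3: a/N = p(1 − f)
- non-starters rate 4–5: (a + k)/N = p(1 − f) + f

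The third minus the second is k/N = f, whatever p is.

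**Size with two non-starters.** 2/20 = 10.0 and 2/15 = 13.3 percentage points.

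**Examples.** The low column holds for ratings of 1 or of 3; the high column uses ratings of 5.

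| N | k | Blank | Low | High | Median (blank / low / high) |
|---|---|---|---|---|---|
| 15 | 2 | 9/13 = 69.2% | 9/15 = 60.0% | 11/15 = 73.3% | 4 / 4 / 4 |
| 20 | 2 | 12/18 = 66.7% | 12/20 = 60.0% | 14/20 = 70.0% | 4 / 4 / 4 |
| 20 | 5 | 10/15 = 66.7% | 10/20 = 50.0% | 15/20 = 75.0% | 4 / 3.5 / 4 |

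With two or three non-starters the median stayed at 4. With four rating low it fell to 3 (N = 15) or 3.5 (N = 20).

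**Can other items identify the non-starters?**
- Leaflet item: a score above zero shows that the exercises were done that week. Zero does not separate a patient who never tried from one who tried and stopped, and it says nothing about diet.
- Protein portions: previous day only, and no question on whether the nutrition advice was tried.
- Study log: counts invitations, refusals, consents and completed follow-ups, not starts.
- Qualitative feedback: may reveal some non-starters, but no count is planned from it.

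Together these narrow the group without defining it.

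**The case against.** Several points on the other side stand.

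- **A non-starter may have a valid answer.** Someone who did not begin because the advice would not fit the day can properly answer 1. The gap concerns those whose reason had nothing to do with difficulty. The data cannot tell the two apart.
- **Non-adherence is examined elsewhere.** Objective (e) covers self-reported adherence at 1 and 3 months, and the 1-month contact also examines the feasibility of following the advice. A reader might infer that the study loses sight of non-starters; the documents do not support that. What is missing is a link from adherence to the ease rating.
- **A skipped item need not vanish.** The log records how many complete the 1-month follow-up, so a blank can be seen against a known count. A rating given without experience cannot be seen in that way.
- **The nurse completes the form with the patient** and could note that the advice was not tried. The right to opt out of questions does not show that skipping is likely. The printed questionnaire is not in the documents, so an unlisted option cannot be excluded.
- **Nothing hangs on a threshold.** The analysis is descriptive, the plan concedes that the sample is too small for a comprehensive analysis, and no percentage rating the advice easy is defined. An exact 95% interval for 10/16 already runs from about 35% to 85%, much wider than 10–13 points.

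These points limit the consequence. They do not supply the missing response.

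**Conclusion.** The point holds in a limited form. As described, the ease item cannot separate a rating based on experience from one that is not, and the other items only partly make up for this. If a percentage is reported, the low-to-high gap equals the non-starters' share of those followed up: 10–13 points for two patients in 15–20. If a median is reported, so few may leave it unchanged. This rests on an assumed number of non-starters and on the questionnaire matching its description in the protocol.

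A reader might go further and call the ease result uninterpretable, or quote a far wider swing. With 16 followed up, 5 never starting and 10 of 11 triers rating it easy, the figure could be 10/16 = 63% or 15/16 = 94%. The documents do not support this as a headline. Both the 31% non-start rate (5/16) and the 91% ease rate among triers (10/11) are invented extremes, and the 4–5 cut is not in the plan. With 2 non-starters and the same 10 easy ratings, the range is 10/16 = 63% to 12/16 = 75%.

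The change is still worth making. It alters what is collected, it costs almost nothing, and later analysis can replace it only in part.

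**What to change.** Add a 'did not try' response outside the 1–5 scale, recorded separately for the exercise advice and the nutrition advice. A single box would misclassify a patient who took up only one of them.

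In the Analysis section, state that the report will give:
1. the number who tried and did not try each component, out of all patients completing the 1-month follow-up;
2. the 1–5 ease rating among those who tried, with both denominators shown. Say whether trying one component is enough to be included.

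Do not impute a rating to non-starters. Counting them all as finding the advice not easy would assign an opinion that some of them do not hold.

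If the forms are already complete, report how many answered the ease item out of those completing 1 month, set this beside the count of zero scores on the leaflet item, and state the limitation. If the printed questionnaire already has such an option, the protocol need only describe it and give the reporting rule.

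The cost is one or two tick-boxes, a short addition to the Analysis section, and a smaller denominator for the ease rating.

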### Target Population

The target population is older adults attending mental health service aged 65 years and older. Age 65 years is the age for referral to the older adult mental health services. The Older adult mental health services provide care and treatment for people aged over 65's who develop new onset functional mental illness such as depression, severe anxiety or those with a diagnosis of dementia with behavioral and psychological problems requiring specialist intervention and care.

Patients with stable mental health conditions (during a recovery phase) will be identified from community mental health clinics and ANP community case load

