### Inclusion criteria

For the purpose of this study service users eligible for the study are:

- (a) Aged 65 years and older

- (b) Cognitive capacity to provide informed consent
- (c) Attending Older adult mental health services
- (d) MH team deem client stable and able to participate in intervention
- (e) Patient independently mobile and living in the community (may use a walk aid)(Clinical frailty Scale  $\leq 5$ )

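### The study log begins at invitation, so it gives uptake among eligible, team-approved patients but cannot show how many others were ineligible or withheld, leaving objective (b) only partly answerable

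*Combined protocol and SAP*

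**What the plan says.** Objective (b), under Aim, is "to test the feasibility of patient recruitment and data collection in the target population". The Target Population section opens with a broad definition: "The target population is older adults attending mental health service aged 65 years and older". It then describes a narrower source of patients: "Patients with stable mental health conditions (during a recovery phase) will be identified from community mental health clinics and ANP community case load".

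Several conditions apply before anyone is invited. Inclusion criterion (d) is "MH team deem client stable and able to participate in intervention". The other inclusion and exclusion criteria concern age, capacity, language, dementia, acute crisis, mobility and Clinical Frailty Scale score. Under Obtaining Consent, "the ANP liaises with the Mental Health team to identify eligible patients and ensure the team are happy for the service user to be approached".

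The study log is described at the end of the outcomes section. Its first entry is the invitation: "A study log is maintained recording the number of eligible patients invited to participate". The remaining entries all follow it: "the number of patients who refused, reasons for refusal, number of patients who consented, number of patients who completed 1-month and 3-month follow-up".

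The Sample size section aims for 15-20 patients. The Analysis section plans descriptive statistics and defines no recruitment rate, denominator or feasibility threshold.

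**The concern.** A recruitment objective framed around a population needs a count of that population, or at least of those considered from it. Here the first recorded number comes after the patients who fail a criterion, and those the team prefers not to have approached, have already dropped out of view. Reasons are recorded only for refusal by the patient.

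If recruitment is slow, the log can show whether invited patients refused. It cannot separate restrictive criteria from team reluctance or from a small caseload. If recruitment goes well, it cannot show what part of the service's patients the result describes. The log is the only planned source of recruitment data, so nothing elsewhere in the plan fills the gap.

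**Working it through.** The plan states no recruitment rate, so there is no figure to reproduce. The check has three parts.

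**1. What is counted at each step**

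| Step | Where described | Counted in the log? |
|---|---|---|
| Patients aged 65+ in clinics and ANP caseload considered | Target Population | No |
| Not eligible, by criterion | Inclusion and Exclusion Criteria | No |
| Eligible, but team not content with an approach | Obtaining Consent | No |
| Eligible, not approached (e.g. target already met) | Not addressed | No |
| Invited | Study log | Yes |
| Refused, with reasons | Study log | Yes |
| Consented | Study log | Yes |
| Completed 1 month and 3 months | Study log | Yes |

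**2. Relation between the two rates**

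consented/considered = (consented/invited) × (invited/considered)

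Since invited/considered cannot exceed 1, consented/invited is never below consented/considered. It exceeds it by the factor considered/invited. The factor is 1.0 if nobody is lost before invitation and rises as more are lost.

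**3. Illustration**

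The consent counts, 15 and 20, are the ends of the recruitment target. The 25 invited and the invited fractions are assumptions, because the documents give no caseload size, exclusion rate or uptake. Considered = 25 / fraction, rounded.

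| Assumed fraction invited | Considered | Factor | 20 consent: 20/considered | 15 consent: 15/considered |
|---|---|---|---|---|
| 100% | 25 | 1.0 | 80% | 60% |
| 90% | 28 | 28/25 = 1.12 | 20/28 = 71% | 15/28 = 54% |
| 70% | 36 | 36/25 = 1.44 | 20/36 = 56% | 15/36 = 42% |
| 50% | 50 | 50/25 = 2.0 | 20/50 = 40% | 15/50 = 30% |
| 30% | 83 | 83/25 = 3.32 | 20/83 = 24% | 15/83 = 18% |

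In every row the log would report the same uptake: 20/25 = 80% (exact 95% CI 59-93%) or 15/25 = 60% (39-79%). The log cannot tell the rows apart. If the denominator is limited to stable patients, fewer are counted as considered and the factor moves towards the top of the table. Patients the team withholds, and those failing other criteria, remain uncounted even then.

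The table also shows why consented/considered is a poor headline rate. Suppose 20 patients consent from 50 considered (40%), and the list holds a further 83 − 50 = 33 eligible patients who are never approached because the target has been reached. The ratio falls to 20/83 = 24% although nobody was less willing or less suitable.

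**The case against.** The strongest reply is that the plan makes no claim the log cannot support. It defines no recruitment rate and never says that consented/invited will be applied to all attenders. As uptake among approached patients, that ratio is sound. All of this stands. The defect is a missing count, not a wrong figure.

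A reader might infer that the study's recruitment rate will overstate feasibility in the target population. The documents do not support that as a prediction. It holds only if someone reads consented/invited as a caseload rate, and by how much is unknown. The percentages in the working rest on assumed counts and are no evidence of a large effect in this service.

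The scope point also stands in part. The Target Population section says that patients with stable conditions will be identified, and acute crisis and moderate to advanced dementia are excluded by design. Counting such patients as failed recruitment would present a scope decision as a feasibility problem. That narrows the gap but does not close it, because a stable, eligible patient whom the team would rather not have approached is still uncounted.

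A reader might also infer two successive team filters. The documents do not establish this: criterion (d) and agreement to an approach may be settled in the same conversation. The point does not depend on it, since the outcome of that conversation is unrecorded either way. Nor do the documents mention a later trial that would inherit the figures. The case rests on objective (b) alone.

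Finally, a tally by criterion could be burdensome if every criterion had to be assessed in patients never approached. That is a fair limit on the fix, and recording only the main unmet criterion meets it.

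**Conclusion.** The concern holds as a gap in data collection. Followed exactly, the plan yields consented/invited and loses the numbers ineligible, withheld and not approached, together with the reasons. Objective (b) is then only partly answerable.

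The size of the gap cannot be obtained from the documents. If consented/invited were read against all attenders aged 65 and over, it would be too high by considered/invited, about 1.1 to 3.3 under assumed invited fractions of 90% to 30%, and 1.0 if nobody were lost before invitation. Given the number of criteria and the approval step, some loss is close to certain. Against stable patients only, the gap is smaller.

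The change should be made because it is cheap and bears on a stated objective. No planned estimate is invalidated.

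**What to change.** Extend the existing log prospectively with an anonymous tally, for the recruitment period, of patients aged 65 and over who were:

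- considered from the clinic lists and ANP caseload;
- not eligible, by main criterion not met, with not stable or in acute crisis shown separately;
- eligible but withheld by the team, with reason;
- eligible but not approached, for example because the target had been reached;
- invited;
- refused, with reason;
- consented;
- completed at 1 month and at 3 months.

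Report the full flow. Give consented/invited with an exact 95% CI and label it uptake among eligible, team-approved patients who were invited. Give the proportions eligible and team-approved among those considered. Do not put a confidence interval on consented/all considered, because that ratio is limited by the 15-20 recruitment target.

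A Clinical Frailty Scale score of 5 falls within the limits given in both the inclusion and the exclusion lists. The two must be reconciled before a tally by criterion is unambiguous.

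The cost is a little extra recording by the ANP during the liaison with the team that already takes place. It needs no extra visits and no identifiable data on non-participants. If recruitment has closed, reconstruct the counts from clinic lists where possible. Otherwise state plainly that the rate describes only invited, team-approved patients.
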